7.2 Statistical Methods

Descriptive Statistics

Univariate descriptive statistics and frequency distributions will be calculated, as appropriate for all variables. Baseline values for demographic, clinical, and outcome variables (primary and secondary) will be tabulated for the treatment groups. These analyses will help identify potential confounding variables to be used as covariates in sensitivity analyses. Distributions across subgroups used in randomization will be compared to assess whether the randomization was successful in equalizing distributions of these prognostic variables across treatment groups. Putative prognostic variables that will be investigated through these descriptive analyses include subjective symptoms of autonomic dysfunction and cardiovascular indices.

Handling of Missing Data

Continuous data monitoring will be done by both study coordinator and the Primary Investigator using computer based systems. Scheduled review of study documentation by study coordinator and Primary Investigator will take place at a frequency of no less than every four to six weeks to assure that all reports are on file, accurate and complete. Prior to data analysis, trends and outliers will be reviewed to consider for potential missing data.

Primary Hypothesis: Treatment of iron deficiency with intravenous iron sucrose in an adolescent with Postural Orthostatic Tachycardia Syndrome will reduce their score on the COMPASS-31 survey by 10 points.

Data will be visually inspected for normality. Group comparisons will include Fisher's exact test for categorical variables and Wilcoxon rank sums for continuous variables. Confidence intervals will be calculated at 95%. All P-values will be 2-sided with values less than 0.05 considered significant. All analyses will be performed on an "intention to treat" basis

Secondary Hypothesis 1: Treatment of iron deficiency with intravenous iron sucrose in an adolescent with Postural Orthostatic Tachycardia Syndrome will reduce heart rate change during tilt table testing from 50 beats per minute to less than 30 beats per minute.

Data will be visually inspected for normality. Group comparisons will include Fisher's exact test for categorical variables and Wilcoxon rank sums for continuous variables. Confidence intervals will be calculated at 95%. All P-values will be 2-sided with values less than 0.05 considered significant. All analyses will be performed on an "intention to treat" basis

7.3 Subject Population(s) for Analysis

Protocol-compliant population: Any subject who was randomized and received the protocol required study drug exposure and required protocol processing

8 Safety and Adverse Events

8.1 Definitions

Unanticipated Problems Involving Risk to Subjects or Others (UPIRTSO)

Any unanticipated problem or adverse event that meets the following three criteria:

- Serious: Serious problems or events that results in significant harm, (which may be physical, psychological, financial, social, economic, or legal) or increased risk for the subject or others (including individuals who are not research subjects). These include: (1) death; (2) life threatening adverse experience; (3) hospitalization inpatient, new, or prolonged; (4) disability/incapacity persistent or significant; (5) birth defect/anomaly; (6) breach of confidentiality and (7) other problems, events, or new information (i.e. publications, DSMB reports, interim findings, product labeling change) that in the opinion of the local investigator may adversely affect the rights, safety, or welfare of the subjects or others, or substantially compromise the research data, **AND**
- Unanticipated: (i.e. unexpected) problems or events are those that are not already described as potential risks in the protocol, consent document, not listed in the Investigator's Brochure, or not part of an underlying disease. A problem or event is "unanticipated" when it was unforeseeable at the time of its occurrence. A problem or event is "unanticipated" when it occurs at an increased frequency or at an increased severity than expected, AND
- Related: A problem or event is "related" if it is possibly related to the research procedures.

Adverse Event

An untoward or undesirable experience associated with the use of a medical product (i.e. drug, device, biologic) in a patient or research subject.

Serious Adverse Event

Adverse events are classified as serious or non-serious. Serious problems/events can be well defined and include;

- death
- life threatening adverse experience
- hospitalization
- inpatient, new, or prolonged; disability/incapacity

• persistent or significant birth defect/anomaly

and/or per protocol may be problems/events that in the opinion of the investigator may have adversely affected the rights, safety, or welfare of the subjects or others, or substantially compromised the research data.

Risk associated with use of Venofer® Information taken directly from the manufacturer[28]:

In efficacy studies in non-dialysis dependent-chronic kidney disease patients (N=139), the most frequent adverse events (\geq 5%) whether or not related to Venofer® administration, were nausea (8.6%), taste disturbance (7.9%), peripheral edema (7.2%), diarrhea (7.2%), dizziness (6.5%), hypertension (6.5%), infusion site pain or burning (5.8%), dyspnea (5.8%), and vomiting (5.0%)

In a randomized, open-label, dose-ranging trial for iron maintenance treatment with Venofer in pediatric patients with CKD on stable erythropoietin therapy at least one treatment-emergent adverse reaction was experienced by 57% (27/47) of the patients receiving Venofer 0.5 mg/kg, 53% (25/47) of the patients receiving Venofer 1.0 mg/kg, and 55% (26/47) of the patients receiving Venofer 2.0 mg/kg. A total of 5 (11%) subjects in the Venofer 0.5 mg/kg group, 10 (21%) patients in the Venofer 1.0 mg/kg group, and 10 (21%) patients in the Venofer 2.0 mg/kg group experienced at least 1 serious adverse reaction during the study. The most common treatment-emergent adverse reactions (> 2% of patients) in all patients were headache (6%), respiratory tract viral infection (4%), peritonitis (4%), vomiting (4%), pyrexia (4%), dizziness (4%), cough (4%), renal transplant (4%), nausea (3%), arteriovenous fistula thrombosis (2%), hypotension (2%), and hypertension (2.1%).

In rare cases, serious hypersensitivity reactions, including anaphylactic-type reactions, some of which have been life-threatening and fatal, have been reported in patients receiving Venofer® (iron sucrose injection, USP). Patients may present with shock, clinically significant hypotension, loss of consciousness, and/or collapse[28].

• Observations to be considered as adverse reactions will include but may not be limited to the following:

Nausea, taste disturbance, peripheral edema, diarrhea, vomiting, dizziness, hypertension, hypotension, infusion site pain or burning, dyspnea, cough, headache, myalgia, arthralgia or pyrexia[28].

• Observations to be considered SERIOUS adverse reactions will include but may not be limited to the following:

Anaphylactic-type reaction, shock, clinically significant hypotension or hypertension or other symptoms leading to hospitalization, surgery, disability, incapacity, birth defect/anomaly or death[28]

All adverse events that do not meet any of the criteria for serious, should be regarded as **non-serious adverse events**.

Other potential risks associated with study participation, but not related to Venofer® use include the following:

- 1. Subjects may have worsening of orthostatic symptoms upon discontinuation of medications as indicated in exclusion criteria. These may include but are not limited to lightheadedness, fainting, headache and nausea
- 2. IV and venipuncture may cause pain, bruising, lightheadedness, and/or fainting, or rarely, infection or infiltration of fluids at the site of the needle stick
- 3. Valsalva maneuver can increase pressure in the chest by 40 mm Hg. There is a potential risk for detached retina and retinal hemorrhage
- 4. Ten minute, 70 degree, head up tilt table test may lead to exacerbation of underlying orthostatic intolerance symptoms, including but not limited to lightheadedness, fainting, headache and nausea
- 5. Confidentiality risk includes the possibility for inappropriate breach of confidentiality

Adverse Event Reporting Period

For this study, the study treatment follow-up period is defined as six months following the last administration of study treatment.

Preexisting Condition

A preexisting condition is one that is present at the start of the study. A preexisting condition will be recorded as an adverse event if the frequency, intensity, or the character of the condition worsens during the study period.

General Physical Examination Findings

At screening, any clinically significant abnormality should be recorded as a preexisting condition. At the end of the study, any new clinically significant findings/abnormalities that meet the definition of an adverse event will also be recorded and documented as an adverse event.

Post-study Adverse Event

All unresolved adverse events will be followed by the investigator until the events are resolved, the subject is lost to follow-up, or the adverse event is otherwise explained. At the last scheduled visit, the investigator will instruct each subject to report, to the investigator, any subsequent event(s) that the subject, or the subject's personal physician, believes might reasonably be related to participation in this study.

Abnormal Laboratory Values

A clinical laboratory abnormality will be documented as an adverse event if iron overload is detected in the post-treatment study visit (Study Visit 2). Subjects found to have iron overload following treatment with the study drug will have medical recommendations made by the

Venofer® use in POTS

Version5

Revised 06/02/16

Primary Investigator. These recommendations may include follow up laboratory and clinical monitoring. With the subject's approval, the Primary Investigator will communicate with the subject's primary care provider for coordination of medical management.

Additional medical recommendations may also be made by the Principal Investigator for the subject if post-treatment laboratory data suggests that the subject remains iron deficient (serum ferritin $\leq 12 \text{ug/L}$) or iron insufficient (serum ferritin $\leq 25 \text{ug/L}$).

Hospitalization, Prolonged Hospitalization or Surgery

Any adverse event that results in hospitalization or prolonged hospitalization will be documented and reported as a serious adverse event unless specifically instructed otherwise in this protocol. Any condition responsible for surgery will be documented as an adverse event if the condition meets the criteria for an adverse event.

Neither the condition, hospitalization, prolonged hospitalization, nor surgery are reported as an adverse event in the following circumstances:

- Hospitalization or prolonged hospitalization for diagnostic or elective surgical procedures for a preexisting condition. Surgery should **not** be reported as an outcome of an adverse event if the purpose of the surgery was elective or diagnostic and the outcome was uneventful.
- Hospitalization or prolonged hospitalization for therapy of the target disease of the study, unless it is a worsening or increase in frequency of hospital admissions as judged by the clinical investigator.

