3.1 General Design

This study is a randomized, double blind, placebo-controlled study to assess the efficacy of a single iron sucrose infusion in adolescents with non-anemic iron deficiency and POTS. Subjects will be screened at outpatient clinic visit appointments. Interested qualified subjects will be consented and offered participation in this trial. Once consent and assent (for patients less than 18 years of age) has been obtained, subjects will be randomized to either treatment or placebo group. Subjects will participate in two on site study visits. During the first visit subjects will complete baseline laboratory studies, tilt table test and study questionnaires. Subjects will then receive the intervention study drug or placebo. The second study visit will occur 7 days \pm 2 days from the first study visit. During the second study visit subjects will repeat laboratory studies, tilt table test and study questionnaires. Follow up questionnaires will be sent to all subjects six months following the initial study visit.

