5.2 Treatment Regimen

One treatment dose will be administered during this study and will take place during the First Study Visit. The treatment dose will be 5 mg/kg of intravenous iron sucrose (maximum dose of 200 mg). Iron sucrose will be diluted to a concentration of 1 mg of elemental iron in 1 mL of NaCl 0.9% (maximum volume of 210 mL). The infusion will be infused at 3.5 mL/minute. A flush of 10 mL of NaCl 0.9% will be given after the infusion.

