 - h. Administration of intervention (study drug OR placebo) followed by 10 mL NaCl 0.9% flush. Patients will have continuous cardiopulmonary monitoring (heart rate, respiratory rate and pulse ox) with blood pressure documented no less than every minutes during the infusion
 - i. Following the intervention, subjects will be monitored for signs and symptoms of intervention hypersensitivity for an additional thirty minutes. Patients will have continuous cardiopulmonary monitoring (heart rate, respiratory rate and pulse ox) with blood pressure documented no less than every fifteen minutes.
- 2. Time estimates for Study Visit One (4-4.5 hours)
 - a. Review of patient information (30 minutes)
 - b. Questionnaire completion (1 hour)
 - c. IV/Venipuncture (20 minutes)

- d. Tilt table test (1 hour)
- e. Intervention (1-1.5 hours)
- f. Subject observation (30 minutes)

6.2 Visit 2

- 3. Study visit TWO will take place 7 days ±2 days following study visit ONE. Study visit TWO will be completed in the Clinical Research Center. The visit will be scheduled such that the tilt table test will be started during the window of 12 pm-4pm. Study visit TWO will include:
 - a. Vital sign screen
 - b. Questionnaire completion
 - i. COMPASS-31 Instrument to assess autonomic symptoms
 - ii. Pediatric Quality of Life Inventory (PedsQL) Version 4.0
 - c. IV/Venipuncture
 - i. Complete blood count
 - ii. Serum ferritin
 - iii. Total serum iron, total iron binding capacity and percent iron saturation
 - iv. Supine and standing catecholamine plasma levels
 - v. Estimated blood volume to be drawn is less than 15 mL
 - d. Ten minute, 70 degree head-up tilt table test which includes measurement of cardiovagal responses via heart rate variation to deep breathing (HRVDB), cardiac and vasomotor adrenergic responses via beat-to-beat heart rate, and blood pressure response with tilt and Valsalva maneuver
 - e. Orthostatic symptom scale assessing orthostatic symptoms during tilt on a visual analog severity scale from 0-10
- 4. Time estimates for Study visit TWO (3-3.5 hours)
 - a. Review of patient information (30 minutes)
 - b. Questionnaire completion (1 hour)
 - c. IV/Venipuncture (20 minutes)
 - d. Tilt table test (1 hour)

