6.3 Mail follow-up

- 5. Follow up by MAIL will take place 6 months after study visit ONE and will include:
 - a. Questionnaire completion
 - i. COMPASS-31 Instrument to assess autonomic symptoms
 - ii. Pediatric Quality of Life Inventory (PedsQL) Version 4.0
 - b. Self-reported current medication list
 - c. Self-reported use of iron treatments (oral or intravenous) from study completion until 6 months post-study completion
 - d. Subjects will be provided a self-addressed, pre-paid envelope to return the materials to the primary investigator
- 6. Time estimate for Mail Follow-Up
 - a. Questionnaire completion (1 hour)

7 Statistical Plan

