8.2 Recording of Adverse Events

At each contact with the subject, the study team must seek information on adverse events by specific questioning and, as appropriate, by examination. Information on all adverse events will be recorded immediately in the source document, and also in the appropriate adverse event section of the subject's research record. All clearly related signs, symptoms, and abnormal diagnostic, laboratory or procedure results will be recorded in this source document.

All adverse events occurring during the study period will be recorded. The clinical course of each event will be followed until resolution, stabilization, or until it has been ultimately determined that the study treatment or participation is not the probable cause. Serious adverse events that are still ongoing at the end of the study period will be followed up, to determine the final outcome. Any serious adverse event that occurs after the study period and will be considered to be at least possibly related to the study treatment or study participation will be recorded and reported immediately.

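### The adverse event reporting period runs six months, but the only scheduled contact after Visit 2 is a mailing with no listed adverse event item

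*Combined protocol and SAP*

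**What the plan says.** All references are to the combined protocol and SAP.

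- **Reporting period.** Section 8.1, under Adverse Event Reporting Period, states that "the study treatment follow-up period is defined as six months following the last administration of study treatment". Section 5.2 states: "One treatment dose will be administered during this study and will take place during the First Study Visit". The period therefore starts on day 0.
- **Duty to ask and record.** Section 8.2 states: "All adverse events occurring during the study period will be recorded". It also requires the team to question subjects specifically about adverse events whenever there is contact, with no exception for contact by mail.
- **Contacts.** Section 3.1: "Subjects will participate in two on site study visits". Section 6.2: "Study visit TWO will take place 7 days ±2 days following study visit ONE". Section 6.3: "Follow up by MAIL will take place 6 months after study visit ONE and will include" COMPASS-31, PedsQL, "Self-reported current medication list" and self-reported iron treatment. The section gives no adverse event or hospitalization item.
- **Schedule of assessments (section 6).** No column has an adverse event row. The month 6 column marks only current medications and the questionnaires.
- **After the last visit.** Section 8.1, under Post-study Adverse Event, has unresolved events followed up. Subjects are told at the last scheduled visit to report later events that they or their own physician think may be connected with the study.

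**The concern.** Visits 1 and 2 are in person, so staff can meet the 8.2 duty by asking, even though sections 6.1 and 6.2 list no adverse event item. A mailing asks only what is printed in it. As listed, the month 6 packet gives no means of doing what 8.2 requires.

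What then remains is narrower than the plan's own scope. Section 8.2 wants all adverse events. Section 8.1 wants worsening of a preexisting condition recorded and, with stated exceptions, hospitalization for an adverse event reported as serious. The standing instruction to subjects covers only events that someone believes are related, and only if the subject volunteers them. Section 8.5 also compares the rate of serious side effects with the labeling, and that rate depends on how completely such events are found.

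**Working it through.** The plan states no coverage figure, so there is none to reproduce.

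**1. Share of the period after Visit 2.** Inputs: the dose is on day 0 (5.2), Visit 2 is on day v = 5, 7 or 9 (6.2), and the period is six months (8.1). The plan does not convert six months to days, so I assume L = 180 to 184 days, with 182.5 as the central value. Share = (L − v) / L.

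| L (days) | v = 5 | v = 7 | v = 9 |
|---|---|---|---|
| 180 | 97.2% | 96.1% | 95.0% |
| 182.5 | 97.3% | 96.2% | 95.1% |
| 184 | 97.3% | 96.2% | 95.1% |

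The central case is (182.5 − 7) / 182.5 = 175.5 / 182.5 = 96.2%. The range is 95.0% to 97.3%.

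**2. What that share means.** It is a calendar share. How much of the period counts as solicited depends on which text is read.

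- Under the 8.2 rule applied to every contact, including the mailing, the whole period is covered on paper (0% uncovered).
- Under listed procedures only, solicitation ends with the 30-minute observation after infusion, because 6.2 lists no adverse event item either (nearly 100% uncovered).
- If Visit 2 is covered by staff asking in person under 8.2, and the packet is sent exactly as 6.3 lists it, 95% to 97% of the period has no listed means of asking.

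The third reading is the practical one, but it rests on the difference between an in-person visit and a printed form. The documents do not draw that distinction.

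**3. Whether the packet can stand in.** The worksheet in 8.3.1 needs, among other things, the event's date, description, relationship, severity and resolution. Symptom scores, quality-of-life scores and a current medication list may hint at an event but do not supply these fields. No rule turns a score change into an adverse event.

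**4. Weight of one missed event.** Section 7.1 plans 15 subjects per group. One missed serious event in the treated group would shift the observed rate by 1/15 = 6.7 percentage points. The documents do not say how many late serious events to expect, so this shows sensitivity only.

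**The case against.** The strongest reply is that 8.2 already settles the matter: it applies to each contact, and nothing prevents a written question from going into the envelope. Section 6.3 says what follow-up will include and does not call its list complete. The section 6 lists are demonstrably incomplete. The schedule marks current medications at both visits and an eligibility check at Visit 2, yet 6.1 omits the first and 6.2 omits both. Absence from a list is thus weak evidence that something will not be done.

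The reply also holds that little would be lost. This is one dose, with a reported serum iron half-life of 8 hours at ages 12 to 16. The primary safety endpoints in 3.3 are infusion monitoring, at least thirty minutes of observation, and iron indices at one week. Section 7 plans no six-month safety analysis. Section 8.1 defines an adverse event as one associated with a medical product, so an instruction about related events is not far from that definition.

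Much of this stands. The main hazards described are watched for at Visit 1, the laboratory check falls at Visit 2, and calendar share is a poor measure of safety information lost. It does not close the gap. For the mailing, 6.3 and the schedule agree, apart from the iron-use item, and neither contains an adverse event question. A packet assembled from them would ask nothing about events, and 8.2 would go unmet at month 6.

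**Conclusion.** Sections 8.1 and 8.2 set a six-month duty to seek and record adverse events. Section 6.3 and the schedule give the only later contact no stated way of meeting it. For about 95% to 97% of the period, the listed procedures leave new events to spontaneous reports of events believed related, with follow-up of events already known. This assumes that the packet is sent as listed, that staff do ask at Visit 2, and that six months is 180 to 184 days. The correction is worth making, but no efficacy or primary safety endpoint depends on it.

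Two stronger readings are tempting, and the documents support neither.

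- A reader might infer that 96% of the period has no solicited safety data. The 8.2 rule covers the mailing on paper, and Visit 2 relies on that same rule, so the figure is only the share of time after Visit 2.
- A reader might infer that reporting would differ by arm once subjects learn their iron status. Section 8.1 says only that recommendations may be made after Visit 2 if ferritin stays low. Nothing establishes that reporting would then differ, in which direction, or by how much.

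**What to change.** Choose one of two routes.

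1. Add to the 6.3 packet a short question on any adverse event or hospitalization since Visit 2, with dates. Add an adverse event row to the schedule, marked at Visit 1, Visit 2 and month 6.
2. Reconcile 8.1 and 8.2 by stating that solicited capture ends at Visit 2 and that later reports, to month 6, are spontaneous only. Any report of six-month safety should then say so.

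The first route costs one extra question on a form already being mailed and one table row. Its limits are recall over nearly six months and dependence on the packet being returned. For subjects who return it, the stretch without a listed question falls to about zero. The second route costs only wording, but gives up active capture after Visit 2.

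### Section 8.1 lets an admission for POTS therapy, planned or not, leave adverse event reporting before relatedness is recorded; the gap is narrow and cheap to close

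*Combined protocol and SAP*

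**What the plan says.** The subsection of 8.1 on hospitalization and surgery opens with a general rule: an adverse event that leads to a hospital stay is to be "documented and reported as a serious adverse event unless specifically instructed otherwise in this protocol". Exceptions follow, introduced by "Neither the condition, hospitalization, prolonged hospitalization, nor surgery are reported as an adverse event in the following circumstances". The first covers diagnostic or elective surgical procedures for a preexisting condition. The second is "Hospitalization or prolonged hospitalization for therapy of the target disease of the study, unless it is a worsening or increase in frequency of hospital admissions", and the decision rests with the clinical investigator.

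Three other parts of 8.1 bear on the same admission:

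- The list of serious adverse reactions to Venofer includes "clinically significant hypotension or hypertension or other symptoms leading to hospitalization" and states no exception.
- A preexisting condition is to be "recorded as an adverse event if the frequency, intensity, or the character of the condition worsens during the study period".
- At the last scheduled visit, subjects are told to report later events that they, or their "personal physician, believes might reasonably be related to participation in this study".

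Section 8.2 adds: "At each contact with the subject, the study team must seek information on adverse events by specific questioning". Section 8.3 has the worksheet completed once an adverse event has been identified, and 8.3.1 makes relationship to the research one of its items. The adverse event reporting period in 8.1 runs for six months after dosing. The last site visit is at day 7 ± 2, and the only later contact is the mailing in 6.3.

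**The concern.** The first exception is limited to elective or diagnostic procedures. The second has no such limit, so on its wording it reaches an unplanned POTS admission days after the infusion. It removes the condition as well as the stay. In practice, the attribution to POTS is then made before anyone documents whether the study contributed.

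That order matters here because study-caused events can look like the target disease. If an admission is put down to usual POTS care and exempted, it is absent from the event log and from any count by arm, and its relationship to the drug, to medication withdrawal or to the tilt test is not recorded. Sections 3.3 and 8.5 both rely on the observed rate of serious side effects, which can only be judged from events that were recorded.

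**Working it through.** No figure in the plan needs reproducing. The check sets the rules side by side and then asks which admissions fall through.

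**1. What brings an exempted stay back.** The second exception yields in one situation: "unless it is a worsening or increase in frequency of hospital admissions as judged by the clinical investigator". It gives no criterion for worsening and no time window. The listed screening items (4.3 and the schedule in section 6) cover demographics, physical examination, laboratory data and medications, but not prior admissions, so an increase in frequency has no listed baseline. The case report form and the safety monitoring plan are not in the documents and may supply one.

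**2. Comparison with the preexisting-condition rule.** That rule counts a change in frequency, intensity or character and does not depend on investigator judgement. It is broader than the exception, and the text does not say how the two fit together.

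**3. Order of steps.** Section 8.3 starts the worksheet from an identified adverse event, and 8.3.1 puts relatedness on that worksheet. A stay not reported as an adverse event would not reach that item. This is an inference; the protocol does not state the order outright.

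**4. Overlap of symptoms.** Entry symptoms in 4.1 include lightheadedness, syncope, headache and nausea.

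- Section 8.1 lists 15 observations to be considered adverse reactions. Three overlap: nausea, headache, and dizziness if counted as lightheadedness. 15 − 3 = 12 do not.
- The paediatric series described in 1.4 had five mild reactions. Two overlap: one headache and one fainting.
- Section 8.1 also names discontinuation of medication and the tilt test as possible causes of worse orthostatic symptoms.

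The overlap is partial but real.

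**5. What is left.** Take an admission after consent for POTS-type symptoms.

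| Investigator's view | Result under 8.1 |
|---|---|
| Worse than before | Reportable |
| More frequent than before | Reportable |
| Neither; usual POTS care | Exempt, and relatedness not recorded |

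Only the third row is a gap. It needs a subject with some history of POTS admissions, or an investigator who sees no worsening.

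**6. Scale.** No admission rate is given, so the number of stays in the third row cannot be derived. With 15 subjects per group (7.1), one iron subject is 1/15 = 6.7 percentage points. That is the weight of any single event in this trial, not a measure of this gap.

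**The case against.** The strongest reply is that 8.1 already handles most of these cases. A subject recruited from outpatient clinics who is admitted with nausea and dizziness soon after an infusion is, on its face, worse, so both the exception's own proviso and the preexisting-condition rule return the event to reporting. Subjects are also questioned at each contact and told to report events they think related. The Primary Investigator is blinded, so misclassification should not favour an arm. All of this stands, and it is why the gap is narrow. It does not cover the stay judged to be usual care. Blinding does not protect an absolute rate from under-counting. The questioning rule in 8.2 has no counterpart in the listed contents of the mailing in 6.3.

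A reader might infer three stronger things that the documents do not support:

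- **That the serious-reaction list and the exception contradict each other.** They do not. The general rule announces that exceptions may follow, and the list concerns reactions to the drug, whereas the exception concerns therapy of the disease. What remains is an unreconciled overlap: the list has no cross-reference, so two careful staff could class the same stay differently.
- **That a post-infusion admission for nausea and dizziness is simply not reportable.** That holds only if the investigator judges it neither worse nor more frequent.
- **That one missed event could decide a stopping rule.** The paediatric serious reaction figures in 8.1 are 5/47 = 10.6% and 10/47 = 21.3%, and one event moves 1/15 = 6.7% to 2/15 = 13.3%, past the first. But 3.3 and 8.5 set no numerical threshold, name no comparator rate, and make an excess only a potential cause for action. The labelled figures also come from repeat dosing in kidney disease.

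The unanticipated-problem route in 8.1 is not confined to adverse events, but events that are part of an underlying disease would probably fall outside it.

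**Conclusion.** The point holds in a limited form. The exemption covers unplanned as well as planned POTS admissions, turns on an investigator judgement with no stated criterion and no listed baseline for frequency, and operates before relatedness is documented. A study-related admission at the subject's usual frequency could go unrecorded.

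The size is small and cannot be put as a number. The conclusion rests on three assumptions: that an exempted stay does not reach the worksheet, that the case report form and monitoring plan do not close the gap, and that some subjects have POTS admissions without evident worsening. The documents do not show that any drug-related harm would in fact be missed. This is a cheap improvement to safety capture, not a defect that threatens the trial's conclusions.

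**What to change.** - In 8.1, limit the target-disease exception to admissions scheduled before consent. Leave the exception for diagnostic or elective surgical procedures as it is.
- Record every other admission as a serious adverse event, from consent or the start of medication withdrawal until six months after the infusion. Starting at the infusion would miss harm from stopping medication.
- Assess relatedness afterwards, while blinded.
- Tabulate admissions by arm descriptively. A test would say little: 3 of 15 against 0 of 15 gives a two-sided Fisher p of 2 × C(15,3)/C(30,3) = 2 × 455/4060 = 0.22.
- State in the serious-reaction list in 8.1 that the exceptions in the hospitalization subsection apply.
- Add a question on hospital admissions and adverse events to the mail pack in 6.3, which lists none although the reporting period runs six months. Visit 2 is already largely covered by 8.2.

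The cost is two wording changes, one added question, a few extra event forms, and some disease-related admissions in the log. Reports to the IRB need not grow, because 8.3.1 sends only directly related events.
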